## 8.2 Randomization, blinding and treatment allocation

Not applicable

## 8.3 Study procedures

### 8.3.1 Investigational endoscopy

For the purpose of the study, preoperative biopsy of the polypectomy site will be done. To allow for sufficient healing of the polypectomy site, an arbitrary period of at least 14 days will exist between the endoscopic resection of the malignant polyp and the second endoscopy. In daily practice, however, it is hard to imagine that the time interval between the two endoscopies could be shorter. First, the pathology report has to be completed, the patient has to be informed, dissemination studies have to be arranged, and the results have to be discussed in a multidisciplinary oncological meeting. If no dissemination has been found and additional resection has been decided on, the patient has to be seen by the surgeon for final planning of the operation. Only after this moment, participation in the study can be offered. The time between the biopsies and surgery should not exceed 4 weeks.

It is convenient to take biopsies from the polypectomy site when a second endoscopy is done for tattooing the polypectomy site or during endoscopic full-thickness resection. In this situation, the burden of participation in the study is zero.

If tattooing has already been done during the first endoscopy (when the malignant polyp was removed), a second endoscopy has to be arranged for the sole reason of participation in the study.

If the malignant polyp was located in the recto-sigmoid colon, a sigmoidoscopy will suffice. Otherwise, the colonoscopy has to be repeated. The details of these investigations are explained in the patient information form. Of course, it remains the decision of the patient whether or not to participate in case a separate endoscopy needs to be arranged. It should be realized, that the patient recently underwent a colonoscopy, so he or she is “experienced” and this is an optimal situation to decide whether or not to participate. It should be kept in mind, that in back-to-back colonoscopy studies, new polyps have been found in 10-25% of cases. This extra colonoscopy check may be of advantage for the patient.

### 8.3.2 Investigational biopsies

Biopsies will be taken through the endoscope with a standard biopsy forceps. The number of biopsies depends on the size of the lesion / scar. In case of a small scar, the neo-epithelial surface of the lesion should be removed by biopsies. However, if more than ten biopsies would be necessary to do this, five biopsies will be taken from the center in a mesh-like fashion at approximately 5 mm intervals. In addition, biopsies will be taken from the edge (if discernible) at 5 mm intervals. Any mucosal irregularities in or around the scar will be biopsied separately. Biopsies should be collected according to pathology standards in formalin.

### 8.3.3 Other procedures

Pathology should be reported according to current standards

After time, all pathology will be independently assessed by [name], pathologist at the National Cancer Institute / Antoni van Leeuwenhoekziekenhuis. The patient needs to consent to this procedure.

Reference assessment will be done without knowledge of the clinical situation.

Local endoluminal, laparoscopic or open resection of the affected colon will take place according to the current standards of care.

### 8.4 Withdrawal of individual subjects

Subjects can leave the study at any time for any reason if they wish to do so without any consequences. The investigator can decide to withdraw a subject from the study for urgent medical reasons. Specific criteria for withdrawal are not applicable

### 8.5 Replacement of individual subjects after withdrawal

The study will continue until the requested amount of subjects is included.

### 8.6 Follow-up of subjects withdrawn from treatment

No treatment is given, so no follow-up will be instigated. These patients are subjected to normal treatment (operation) as has already been planned.

### 8.7 Premature termination of the study

It is possible that at an earlier inclusion stage it may be seem that the sensitivity of biopsies is low. However, a low sensitivity, e.g. 70%, may still be useful as it may substantially reduce the post-test probability to below the probability of postoperative death in high risk groups (this is currently difficult to predict, as it is dependent on the observed prevalence of residual tumor, the sensitivity of the biopsy, and the postoperative mortality in the study group). Thus a low observed sensitivity at an earlier inclusion stage shall be no reason to stop the inclusion prematurely.

It can be contemplated to stop inclusion if the observed sensitivity is very high, “definitely” not inferior to 95%. In that case, the negative predictive value of biopsies is so high that is may seem to be unethical to continue operating on these patients if biopsies show no residual cancer. However, the risk of a false conclusion (type I-error) should be extremely small: we pre-state a probability less than 0.0005. For such limits, table 1 is applicable. Results will be evaluated after every inclusion of 20 patients with residual tumor in biopsy. The study will be stopped if the limit has been reached at two evaluations.

Number of patients with residual cancer at operation	Limit for rejecting the 0-hypothesis with a type I error risk < 0.0005
20	19 (95%) (all are positive)
40	39 (97.5%) (all are positive)
60	59 (98.3%) (all are positive)
80	78 (97,5%)
100	97 (97%)
120	116 (96.67%)
140	135 (96.43%)
160	155 (96.89%)
180	173 (96.11%)

Table 1: numbers of patients with tumor in the resection specimen and observed sensitivity limits at which it can be concluded that sensitivity is no inferior to 95% with a probability of a type I error < 0.0005. If these limits are reached on two evaluation points, the study will be prematurely terminated.

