#### 4.4 Sample size calculation

The overarching goal is to investigate whether second-look endoscopic biopsies after resection of a malignant polyp with uncertain pathological completeness can be used as a screening instrument to aid in the clinical decision whether rescue surgery should be performed or not. The specificity of second-look biopsies from the polypectomy site for residual malignancy is estimated to be near 100%, as it is reasonable to state that no person without residual malignancy in the bowel wall is likely to have tumor in second look biopsies, in other words, the false-positive rate will be approximately zero.

Accordingly, sample size calculations will be done on the basis of sensitivity, i.e. the number of patients with positive second-look biopsies divided by the number of patients who do have residual tumor in the resected specimen. We state that sensitivity should be at least 95% to be clinically relevant. A non-inferiority approach can be used to calculate sample size. In that case, the null-hypothesis states that sensitivity is significantly inferior to 95%. Because proof of exact equality to 95% is impossible, a pre-stated margin of non-inferiority of -5% (90% in our study) is accepted.

The distributions of the probabilities belonging to the null- (around  $p = 0.90$ ) and alternative (around  $p = 0.95$ ) hypothesis is binomial but may be approximated by a normal distribution for sample size calculation.

Using the normal approximation, it can be calculated that 184 patients need to be included to achieve a power of 0.80 with and a probability of falsely accepting biopsies as non-inferior ( $\alpha$ ) of 0.05.

Using binomial distributions, it can be shown that 194 patients need to be included to achieve this goal. We will use the latter number for a robust estimate of sample size.

We estimate incomplete data and / or refusal to participate in 1 out of 10 patients invited.

This calculates to a number of 216 patients with residual tumor to be invited. Depending on the prevalence of residual tumor, which is estimated to vary between 10 and 30% (average 20%) of all patients, a total of 1080 patients fulfilling the inclusion criteria need to be invited to accomplish this number.

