10.3 Interim analysis

As is described in chapter 8.7.

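### The early-stopping limits in Table 1 do not give a type I error below 0.0005; as printed, the rule can stop at 39 of 40, where the error is 8%

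*Protocol*

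**What the plan says.** Section 8.7 of the protocol describes stopping if observed sensitivity is very high. It asks for a very small type I error and presents Table 1 as the limits that achieve this: "we pre-state a probability less than 0.0005. For such limits, table 1 is applicable". Looks come after every 20 patients, from 20 to 180, and "The study will be stopped if the limit has been reached at two evaluations". The limits are 19/20, 39/40, 59/60, 78/80, 97/100, 116/120, 135/140, 155/160 and 173/180. The first entry reads "19 (95%) (all are positive"), and the rows for 40 and 60 carry the same note beside 39 and 59.

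Section 4.4 defines the hypotheses. The target is 95%, and "a pre-stated margin of non-inferiority of -5% (90% in our study) is accepted", so the null lies at 0.90 and the alternative at 0.95. The final analysis has α = 0.05, power 0.80 and 194 patients with residual tumor. Section 10.3 adds nothing on interim analysis beyond "As is described in chapter 8.7".

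**The concern.** Two things stand out before any calculation. First, 19 of 20, 39 of 40 and 59 of 60 are not all-positive results, so the first three rows contradict their own note. Second, the required percentage rises from 96.43% at 140 to 96.89% at 160 and then falls to 96.11% at 180, which one consistent criterion would not be expected to produce.

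The more serious doubt is whether 20 or 40 patients can ever exclude a sensitivity of 0.90 at the 0.0005 level. Section 8.7 wants an extremely small error because stopping would rest on the view that operating on biopsy-negative patients may no longer be ethical. If the limits are too loose, the study could end after 40 informative patients on evidence that would not pass its own final test.

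**Working it through.** **Inputs.** Null p0 = 0.90, alternative p1 = 0.95, final α = 0.05, power 0.80, n = 194 (section 4.4). Limits, look schedule, two-evaluation rule and claimed error of 0.0005 (section 8.7).

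**Check that 0.90 is the null the protocol used.** The one-sided normal approximation gives

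n = [(1.645·√(0.9·0.1) + 0.8416·√(0.95·0.05)) / 0.05]² = [(0.4935 + 0.1834) / 0.05]² = 183.3, so 184.

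This is the protocol's figure. At n = 194 with success defined as X ≥ 182, the exact binomial α at 0.90 is 0.0427 and the power at 0.95 is 0.824, which agrees with the stated 194. The protocol does not print the cut-off of 182. It is the smallest count that keeps α below 0.05 (181 gives 0.073).

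**Error at each printed limit,** P(X ≥ limit | n, p):

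| Limit | p = 0.90 | p = 0.95 |
|---|---|---|
| 19/20 | 0.392 | 0.736 |
| 39/40 | 0.0805 | 0.399 |
| 59/60 | 0.0138 | 0.192 |
| 78/80 | 0.0107 | 0.231 |
| 97/100 | 0.0078 | 0.258 |
| 116/120 | 0.0056 | 0.278 |
| 135/140 | 0.0040 | 0.294 |
| 155/160 | 0.0009 | 0.184 |
| 173/180 | 0.0020 | 0.318 |

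No row is below 0.0005. If the caption is read as testing against 0.95 itself, every row is worse.

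**Smallest usable look.** With all results positive the tail is 0.9ⁿ: 0.122 at 20, 0.0148 at 40 and 0.0018 at 60. Solving 0.9ⁿ < 0.0005 gives n > ln(0.0005)/ln(0.9) = 72.1. At least 73 patients are needed, so no limit can work at the first three looks.

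**Effect of requiring two evaluations.** The looks are cumulative. A count of 39 or 40 out of 40 means at most one miss, so at least 19 of the first 20 were positive. The limit at 20 is therefore always met when the limit at 40 is met, and the rule stops at n = 40 with probability

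0.9⁴⁰ + 40·0.1·0.9³⁹ = 0.0148 + 0.0657 = 0.0805.

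**Whole rule.** An exact recursion over the nine looks, stopping at the second hit and otherwise testing X ≥ 182 at 194, gives at true sensitivity 0.90:

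| Reading of Table 1 | False stop | Final test | Overall |
|---|---|---|---|
| Counts as printed | 0.0849 | 0.0272 | 0.112 |
| All positive at 20, 40, 60 | 0.0230 | 0.0347 | 0.058 |
| Every limit must be exceeded | 0.0166 | 0.0381 | 0.055 |

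The stopping errors are about 170, 46 and 33 times 0.0005. Requiring two consecutive hits lowers the first only to 0.082. At a true sensitivity of 0.92 the printed counts stop early in 18% of trials (7.5% and 4.8% on the other two readings).

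**Possible origin.** A one-sided Wald test, with the variance taken from the observed proportion, gives the printed limits at 60, 80, 100 and 120. It gives 134, 153 and 172 at the last three looks, and it does not support the rows at 20 and 40. No single test that was tried reproduces the whole table.

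**The case against.** The best defence is that the 8% uses the reading least kind to the protocol. The note in the first three rows can be taken as binding, or the printed number as one to be exceeded, which would make the note correct. Then 39 of 40 does not stop the study, the error at n = 40 is 0.0148, and 40 of 40 would reject 0.90 at the 0.05 level. If limits must be exceeded, the row at 160 becomes 156/160 with a tail of 0.00024, which does meet the claim. The overall inflation is then modest, 0.055 to 0.058 against 0.05, and it depends on the inferred final cut-off. Section 8.7 also opens by saying only that stopping may be considered, and it sets no rule for practice.

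Part of this stands: the size of the error depends on the reading and should be given as a range. But the printed counts have the stronger claim. The counts and their matching percentages are both printed, and the text says that a limit is reached, not exceeded. The same section then states without condition that the study will stop. Even on the most favorable reading the stopping error is 33 times the pre-stated value.

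**Conclusion.** The concern holds. Table 1 does not deliver the claimed error of 0.0005 on any reading. The probability of stopping falsely at a true sensitivity of 0.90 is 0.085 for the printed counts and 0.017 to 0.023 on the stricter readings. The overall type I error is 0.112, or 0.055 to 0.058, where section 4.4 states 0.05. A stop at 39 of 40 would come with p = 0.080, which does not reject 0.90 even at the ordinary final level.

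The result assumes p0 = 0.90 (stated), looks at exactly 20, 40, …, 180 patients with residual cancer at operation (the table's count), and, for the overall error only, a final exact test at 182 of 194 (inferred). The stopping errors do not depend on the last assumption. This should be corrected before the rule is used.

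**What to change.** Replace Table 1 with exact limits under p0 = 0.90 and delete the looks at 20, 40 and 60:

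| n | Stop if at least | P(X ≥ limit given 0.90) |
|---|---|---|
| 80 | 80 | 0.00022 |
| 100 | 99 | 0.00032 |
| 120 | 118 | 0.00033 |
| 140 | 137 | 0.00030 |
| 160 | 156 | 0.00024 |
| 180 | 175 | 0.00019 |

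One positive fewer breaks 0.0005 in every row. With the two-evaluation rule kept, the cumulative stopping error is 0.00038. Adding the final test (0.0424) gives an overall type I error of 0.043, and overall power at 0.95 is 0.824. The caption should name 0.90 as the null, say that a limit is met at or above the count shown, and drop the note about all-positive results. The text of section 8.7 counts looks by tumor in the biopsy while the table counts cancer at operation. That is a separate inconsistency, but these limits apply only to the latter.

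The alternative is to keep the present limits, replace the 0.0005 by their true error and lower the final α. This cannot bring the overall error down to 0.05 with the counts as printed, because the stopping error alone is 0.085. It could work only on the stricter readings.

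The cost is one table and its caption. Early stopping becomes rarer: at a true sensitivity of 0.95 it occurs in 10% of trials, against 54% with the printed counts (40% or 27% on the stricter readings). No patients are needed beyond the planned 194.

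### Section 8.7 schedules the interim looks by counting biopsy-positive patients, but the Table 1 limits are indexed on patients with cancer in the resection specimen, so most looks match no row

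*Protocol*

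**What the plan says.** Protocol section 8.7 allows inclusion to stop early if the observed sensitivity is very high. The timing of the looks is set by "Results will be evaluated after every inclusion of 20 patients with residual tumor in biopsy". The action is "The study will be stopped if the limit has been reached at two evaluations", and for the risk of a false conclusion "we pre-state a probability less than 0.0005".

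The limits are in Table 1. Its first column is headed "Number of patients with residual cancer at operation" and runs 20, 40, ..., 180. Its caption describes "numbers of patients with tumor in the resection specimen and observed sensitivity limits".

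Section 4.4 defines sensitivity as "the number of patients with positive second-look biopsies divided by the number of patients who do have residual tumor in the resected specimen". Section 10 uses the same structure, with tumor in the bowel wall and/or resected lymph nodes as the denominator. Section 10.3 on interim analysis adds only "As is described in chapter 8.7", so nothing elsewhere reconciles the two counts.

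**The concern.** The trigger counts positive biopsies; the table counts positive specimens. These are the numerator and the denominator of the same proportion, and they agree only if no cancer has been missed. Whenever the biopsies have missed a cancer, the denominator at the look exceeds the multiple of 20 for which a limit is printed.

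Whoever runs the look must then improvise: use the nearest row, apply the row's percentage to a different count, or wait for the next row. These choices can give different answers on the same data, and the first three rows leave room for one miss at most. An early stop would support the claim that sensitivity is not inferior to 95%, so the rule should leave no choice to be made after the data are seen.

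**Working it through.** **Inputs**
- Trigger: 20k biopsy-positive patients at look k (section 8.7).
- Limits (section 8.7, Table 1), as specimen-positive count: limit. 20: 19; 40: 39; 60: 59; 80: 78; 100: 97; 120: 116; 140: 135; 160: 155; 180: 173.
- Null sensitivity 0.90 and alternative 0.95 (section 4.4).
- False positives: section 4.4 expects that "the false-positive rate will be approximately zero", so every biopsy-positive patient is taken to be specimen-positive.

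**Step 1. Confirm the null value.** The one-sample normal approximation, one-sided 5%, power 80%, is ((1.645·√(0.90·0.10) + 0.842·√(0.95·0.05))/0.05)² = 183.3, hence the protocol's 184. The exact binomial at 194 rejects at 182 or more, with error 0.0427 and power 0.824. The protocol's null is therefore 0.90.

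**Step 2. Try to reproduce the stated type I error of Table 1 at its own counts.** For each row, take the binomial tail at p = 0.90, reading the limit r as at least r or as more than r. The note that all patients are positive in the first three rows fits only the second reading.

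| Specimen-positive n | Limit r | P(X ≥ r) | P(X > r) |
|---|---|---|---|
| 20 | 19 | 0.392 | 0.122 |
| 40 | 39 | 0.080 | 0.015 |
| 60 | 59 | 0.0138 | 0.0018 |
| 100 | 97 | 0.0078 | 0.0019 |
| 160 | 155 | 0.00091 | 0.00024 |
| 180 | 173 | 0.0020 | 0.00067 |

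The stated figure (< 0.0005) is not reproduced. Of all nine rows, only 160 on the stricter reading falls below it. At 20, 40 and 60 no limit could, since even all-positive has probability 0.122, 0.015 and 0.0018. This fault exists whatever triggers the looks.

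**Step 3. Specimen-positive count at a biopsy-triggered look.** Let s be the true sensitivity. At look k the count is N = 20k + F, where F is the number of missed cancers accrued by the time of the 20k-th positive biopsy. F is negative binomial, so the mean of N is 20k/s.
- s = 0.90: 20/0.90 = 22.2; 40/0.90 = 44.4; 60/0.90 = 66.7; ...; 180/0.90 = 200.
- s = 0.95: 20/0.95 = 21.1; 40/0.95 = 42.1; 60/0.95 = 63.2; ...; 180/0.95 = 189.5.

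At s = 0.90 the ninth look is expected at 200 specimen-positives, beyond the planned 194.

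**Step 4. Chance that the count falls on row k.** This needs F = 0, with probability s^(20k).

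| Look | s = 0.90 | s = 0.95 |
|---|---|---|
| 1 (N = 20) | 0.90^20 = 12.2% | 0.95^20 = 35.9% |
| 2 (N = 40) | 0.90^40 = 1.5% | 0.95^40 = 12.9% |
| 3 (N = 60) | 0.90^60 = 0.2% | 0.95^60 = 4.6% |

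At later looks the chance that N is any multiple of 20, including values above 180 that have no row, is at most 8.4% at s = 0.90 and 1.7% at s = 0.95.

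**Step 5. After alignment.** Looks at 20, 40, ..., 180 specimen-positive patients fall on the nine rows exactly. An exact recursion over the nine looks at s = 0.90 gives a probability of reaching the limit at two of them of 0.085 (at least r) or 0.017 (more than r).

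**The case against.** The strongest reply is that this is a slip of one word. The header, the caption and the definitions in sections 4.4 and 10 all point to the specimen, and a team reading the trigger that way would land on the rows. At high sensitivity the shift at the first look is about one patient. That stands, and it makes this a wording repair rather than a design failure. The sentence is still the only instruction on when to look.

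Three stronger readings are tempting, and the documents do not support them.

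- *The study would be certain to stop at the second look.* This holds only if 20k positive biopsies are set against row k as if they were the denominator (20 against 19, 40 against 39). That requires ignoring the table header, its caption and the section 4.4 definition together. The sentence says when to evaluate, not on whom to compute sensitivity.
- *The biopsy trigger is what spoils the error rate.* Table 1 also prints its limits as percentages. Applying those at biopsy-triggered looks gives a probability of two hits of 0.077 at sensitivity 0.90, against 0.085 at the fixed rows with limits read as at least r. On that reading the trigger does not raise the risk. On the stricter reading the fixed-row figure is 0.017, but the comparison is then not like for like: 20 of 21 is 95.2%, which passes the printed 95%, while the all-positive note allows no miss. That conflict lies within the table. Nor are the limits sound at fixed counts, as Step 2 shows.
- *Missed cancers awaiting surgery are left out, biasing the look upward.* Section 8.3.1 allows up to four weeks between biopsy and surgery. But section 10 counts a patient as evaluable only with both biopsies and a resection specimen, and section 8.3.1 also allows biopsies during full-thickness resection. The bias needs an assumption that the protocol does not make.

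**Conclusion.** The inconsistency is real and lies within one section: looks are scheduled on the numerator and limits indexed on the denominator. As written, the first look matches its row with probability 12% (sensitivity 0.90) or 36% (0.95), the second with 1.5% or 13%, and later ones seldom. The stopping rule therefore cannot be applied as printed at most looks. These figures assume independent patients, constant sensitivity and the protocol's own expectation of practically no false-positive biopsies.

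The fault is in the timing sentence; Table 1 uses the right denominator. The finding does not show that the trigger inflates the risk of a false stop. The gap between the stated 0.0005 and what Table 1 delivers is a separate fault that remains after this one is repaired. The point should be corrected, and the correction is small.

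**What to change.** In section 8.7, change the trigger so that it counts patients with residual tumor in the resected specimen, using the section 10 definition (bowel wall and/or resected lymph nodes). State that each look uses the first 20, 40, ..., 180 consecutive evaluable patients with residual tumor, evaluable meaning that biopsies and specimen are both available, ordered by a fixed date such as the biopsy date. Section 10.3 needs no change because it refers back.

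The cost is one or two sentences, and a look may wait a few weeks for specimen results. It would not help to hold each look until everyone biopsied by then has a specimen. At the protocol's upper figures, 520 × 4/52 = 40 patients could be pending. At 20% prevalence about 8 of them would be specimen-positive, which would move the first look to about 28 and off its row again.

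Separately, correct the stated type I error or the limits. Aligning the trigger leaves a probability of 0.085 or 0.017 of stopping at sensitivity 0.90, not below 0.0005. State also whether a limit is met at the printed number or only above it.

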## **10 Statistical analysis**

All statistical analyses will be done in the Deventer Hospital, with support of the local department of clinical epidemiology ([name]). Final approval will be obtained from the department of biostatistics and epidemiology at the Erasmus Medical Center ([name]). In principle, sensitivity will be calculated by dividing the number of patients with positive biopsies by the number of patients with tumor in the bowel wall and / or resected lymph nodes. Separate analysis will be done for bowel wall affection (as opposed to lymphatic spread) only.

The above-mentioned factors of potential influence will be studied on associations with the presence or absence of tumor in the bowel wall and / or resected lymph nodes. This will be done by using an independent samples *t*-test in the case of continuous normally distributed variables; by nonparametric test (e.g. Mann-Whitney U-test) in case of non-normally distributed ordinal variables; by Chi-Square statistics in case of categorical variables and by multiple logistic regression to investigate multiple associations.

Missing data will be dismissed from the analysis: the main issue is, whether there are preoperative biopsies and a resection specimen. If one of both fails, the loss will be compensated by the inclusion of another patient, as long as the number of evaluable patients is not reached.

NL51461.078.15 / NCT02328664 Scar biopsies after malignant colorectal polypectomy of uncertain radicality

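### The study stops early only for a very high observed sensitivity, and section 10 then reports the plain ratio, which is biased upward under the Table 1 limits as printed

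*Protocol*

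**What the plan says.** Section 4.4 sets the target: "We state that sensitivity should be at least 95% to be clinically relevant", and "a pre-stated margin of non-inferiority of -5% (90% in our study) is accepted". The planned number is 194 patients with residual tumor.

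Section 8.7 rules out stopping for a low observed sensitivity and allows stopping for a very high one. Table 1 lists limits at 20, 40, …, 180 patients with residual cancer, and "The study will be stopped if the limit has been reached at two evaluations". Beside the limits at 20, 40 and 60 (19, 39 and 59) it adds a remark that all are positive, which does not match the printed counts.

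Section 10 gives the estimator: "sensitivity will be calculated by dividing the number of patients with positive biopsies by the number of patients with tumor in the bowel wall" and/or the resected lymph nodes. It does not distinguish a study that ran to 194 from one that stopped early. Section 10.3 says only "As is described in chapter 8.7". No section gives an adjusted estimate, or an interval of any kind, for use after an early stop.

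**The concern.** A plain proportion is unbiased at a fixed sample size. It is not unbiased when sampling ends because that proportion was high and continues otherwise. Here stopping is on the high side only, and the early evaluations are small, so one miss more or less decides the outcome.

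Section 8.7 justifies the stop by the negative predictive value, and it also weighs post-test probability against postoperative death. Both depend on the miss rate (1 − sensitivity). At a miss rate near 5%, an upward bias of one to three points in sensitivity is a large relative error.

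**Working it through.** **Inputs.** Null sensitivity 0.90, alternative 0.95, alpha 0.05, power 0.80 and 194 patients (section 4.4). Limits 19/20, 39/40, 59/60, 78/80, 97/100, 116/120, 135/140, 155/160 and 173/180, with a stop at the second evaluation that meets its limit (section 8.7). Plain ratio (section 10).

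**The plan's own figure.** n = [(1.645·√(0.9·0.1) + 0.842·√(0.95·0.05))/0.05]² = 183.3, so 184, one-sided. With exact binomials, 194 patients and at least 182 positives give alpha 0.043 and power 0.824. Both planned numbers reproduce.

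**Readings of the rule.** The main figures read each limit as 'at least' and count any two evaluations. Evaluations are indexed by residual cancer at operation, as in the Table 1 heading. Reading A uses the printed counts throughout. Reading B requires all positive at 20, 40 and 60, and the printed counts afterwards.

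**A step that can be checked by hand.** Under A, 39 or more of 40 implies 19 or more of the first 20, so the rule is met at n = 40 with probability 0.95⁴⁰ + 40·0.95³⁹·0.05 = 0.129 + 0.271 = 0.399. Such a study can report only 39/40 or 40/40, a miss rate of 2.5% or 0%. Under B the probability is 0.95⁴⁰ = 0.129, and the report is 100%.

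**Full calculation.** Exact recursion over evaluations at 20, 40, …, 180; studies that do not stop continue to 194. True sensitivity 0.95:

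| | Reading A | Reading B |
|---|---|---|
| Probability of early stop | 0.543 | 0.404 |
| Mean ratio, stopped studies | 97.9% | 98.1% |
| Mean miss rate, stopped studies | 2.1% | 1.9% |
| Mean ratio, studies reaching 194 | 94.1% | 94.2% |
| Mean ratio, all studies | 96.2% | 95.8% |
| Mean miss rate, all studies | 3.8% | 4.2% |

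The all-study means follow as 0.543·97.9 + 0.457·94.1 = 96.2 and 0.404·98.1 + 0.596·94.2 = 95.8. A simulation of 400,000 studies under A gave 0.543 and 97.9%.

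**Other readings.** Requiring two consecutive evaluations gives early stops in 49% (A) or 34% (B) of studies, with miss rates at a stop of 1.9% or 1.7%. Reading the limits as 'more than' gives 27% (any two) or 23% (consecutive), with 1.2% or 0.9%. Over all six readings the all-study overstatement is 0.6–1.2 points.

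**Other true values (reading A).** At 0.93 and 0.90, 26% and 8.5% of studies stop, again reporting 97.9% on average. At 0.97, 89% stop and report 98.2%: miss rate 1.8% against 3.0%, a ratio of 0.60.

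**Post-test risk.** With 20% prevalence (section 4.4), specificity taken as 100% and miss rate m, the risk after a negative biopsy is 0.2m/(0.2m + 0.8). For m = 0.05 this is 0.010/0.810 = 1.2%. For m = 0.021 it is 0.0042/0.8042 = 0.5%.

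**Dependence on Table 1.** Under 0.90, the probability of reaching the printed limit at a single evaluation is 0.392 at 19/20, 0.080 at 39/40, 0.014 at 59/60 and 0.002 at 173/180, all above the stated 0.0005. All positive at 20, 40 and 60 gives 0.122, 0.015 and 0.0018, still above it. Limits that do meet 0.0005 at each evaluation are 80/80, 99/100, 118/120, 137/140, 156/160 and 175/180, with none possible at 20–60. With those limits and true 0.95, 10% of studies stop and report 98.2% on average, and the all-study mean is 95.1%. Stage-wise median-unbiased estimates are then close to the raw ratio:

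| Stop at | Raw | Median-unbiased |
|---|---|---|
| 99/100 | 99.0% | 99.2% |
| 118/120 | 98.3% | 98.3% |
| 156/160 | 97.5% | 97.4% |
| 175/180 | 97.2% | 97.0% |

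With the limits as printed (A), the same method moves 39/40 from 97.5% to 95.8%, and 97/100 from 97.0% to 95.3%.

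**The case against.** The strongest objection is that the fault lies in Table 1. Once its limits meet 0.0005, the all-study bias is about 0.1 point and the adjusted estimate hardly differs from the raw one. This stands. A reader might infer that the estimation problem is separate from whether the limits are right, because an early stop at true 0.95 still reports about 98.2% under corrected limits. The documents do not support that. The remaining excess is conditional on stopping, and the adjusted estimate does not remove it, being median-unbiased over all studies only.

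A reader might also infer that the published miss rate would in general be more than halved. That holds on average for studies that stop at a true sensitivity of 0.95. Over all studies the miss rate falls from 5% to 3.8–4.2%. If misses in stopped studies are pooled over all their tumors (reading A), the miss rate is 2.5%, about half.

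A third tempting inference is that a stop at 97/100 would fail the 90% margin once sequential testing is allowed for. Under reading A the stage-wise one-sided lower bound is 88.6%, but under reading B it is 91.7% (median-unbiased estimate 96.4%). Section 10 states no bound, so there is no planned bound to contradict.

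Finally, section 10 speaks of its estimator as applying in principle, and adjusted estimates are often left to an analysis plan, which is not shown. That softens the point. But the protocol itself fixes the rule, the schedule and the estimator, and section 10.3 refers back to 8.7 without changing the estimator.

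**Conclusion.** The point holds for the limits as printed. At true sensitivity 0.95, about 40–54% of studies stop early and report about 98% on average (miss rate about 2% instead of 5%). Over all studies the overstatement is 0.8–1.2 points. These ranges cover readings A and B, with limits read as 'at least', any two evaluations, evaluations counted by residual cancer at operation, and otherwise a full 194. The figures change with the true sensitivity and with the reading.

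The size follows from Table 1. If its limits are corrected to 0.0005 against 0.90, little bias is left for an adjusted estimate to correct. The point is therefore a reporting safeguard that belongs with the repair of Table 1 and does not replace it.

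**What to change.** Add a paragraph to section 10. If inclusion stops under 8.7, report a median-unbiased estimate of sensitivity with an exact bound from stage-wise ordering over the planned evaluations. Show it beside the raw ratio, and label the raw ratio as unadjusted for early stopping. Compute any negative predictive value or post-test risk from the adjusted estimate. State that the adjustment is median-unbiased over all studies and not conditional on having stopped.

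The calculation needs one definite rule. Section 8.7 should therefore say what the all-positive remark means, whether a limit is met by reaching or by exceeding it, and whether the two evaluations must be consecutive.

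The cost is a paragraph and a short calculation, with no extra patients or procedures. The downside is a slightly less favourable reported sensitivity after an early stop.
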